9.3.8 Fibroscan

Where available, Fibroscan will be performed as per institution standard practice at the times indicated in the Schedule of Assessments ([Table 1](#)).

9.3.9 Magnetic Resonance Cholangiopancreatography

Magnetic resonance cholangiopancreatography or ECRP will be performed during the Screening Visit and is only applicable for patients without results available < 6 months prior to the Screening Period. A confirmatory MRCP is also required if a historical MRCP or ECRP is not completed within 6 months of the Screening Period.

9.3.10 MELD Score

The MELD Score will be calculated as follows:

$$\text{MELD Score} = 9.57 \times \ln(\text{creatinine mg/dL}) + 3.78 \times \ln(\text{total bilirubin mg/dL}) + 11.2 \times \ln(\text{INR}) + 6.43$$

The MELD Na Score will be calculated as follows:

$$\text{MELD Na Score} = \text{MELD} - \text{Na} - [0.025 \times \text{MELD} \times (140 - \text{Na})] + 140$$

Laboratory values less than 1.0 will be set to 1.0 and serum creatinine values greater than 4.0 mg/dL (equivalent to 353.6 µmol/L) will be set to 4.0 for calculation of the MELD score.

9.3.11 Stool Samples

For patients with IBD, stool samples will be collected (at home) prior to each study visit beginning with Visit 2 for assessment of faecal calprotectin. Stool sampling kits will be provided to patients for at-home collection.

9.3.12 Assessment of Pruritus

At the Screening Visit, site staff will assess pruritus by having patients respond to a dichotomous yes/no question asking if they have “experienced pruritus in the past 7 days.” For patients reporting pruritus, a pruritus NRS ([Appendix 1](#)) will be completed

within the Patient Diary daily throughout the study ([Table 1](#)). The pruritus NRS contains an 11-point scale asking patients to rate their worst pruritus in the past 24 hours.

9.3.13 Assessment of Fatigue

All patients will complete a fatigue NRS ([Appendix 1](#)) within the Patient Diary daily throughout the study ([Table 1](#)).

The fatigue NRS will be used to assess fatigue daily throughout the study. The fatigue NRS contains an 11-point scale asking patients to rate their worst fatigue in the past 24 hours.

9.3.14 Assessment of Sleep Disturbance

All patients will complete a sleep disturbance NRS ([Appendix 1](#)) within the Patient Diary daily throughout the study ([Table 1](#)).

The sleep disturbance NRS will be used to assess sleep disturbance throughout the study. The sleep disturbance NRS contains an 11-point scale asking patients to rate their difficulty falling and staying asleep the previous night.

9.3.15 Assessment of Mood

All patients will complete a Likert scale ([Appendix 1](#)) in the Patient Diary daily throughout the study ([Table 1](#)).

The mood Likert scale will be used to assess mood throughout the study. The mood Likert scale contains a 5-point scale asking patients to rate their feelings of sadness or depression in the past 24 hours.

9.3.16 Special Situations

Certain safety events are defined by regulatory authorities as special situations and require reporting. These special situations include:

- Overdose of study medication ([Section 9.3.17](#))
- Pregnancy ([Section 9.3.18](#))
- Suspected abuse/misuse of study medication
- Medication error involving the study medication
- Drug-drug interaction

Special situations should be reported within 24 hours of awareness on the Special Situations eCRF, whether or not they result in an AE/SAE. If a Special Situation results in

an AE or SAE, the event should also be reported on the AE/SAE eCRF following the process described in [Section 9.3.4.8](#).

9.3.17 Overdose

The no-adverse-effect dose level in the most sensitive species CCI

CCI

CCI

The risk of overdose in this study is expected to be minimal. Patients exposed to higher than proposed doses should be observed and supported appropriately.

In the event of an overdose, the Investigator should:

- Contact the medical monitor immediately.
- Evaluate the participant to determine, in consultation with the medical monitor, whether study intervention should be stopped.
- Perform PK samples until study intervention can no longer be detected systemically.
- Closely monitor the participant for any AE/SAE and laboratory abnormalities until study intervention can no longer be detected systemically and until AE/SAE and laboratory abnormalities resolve or stabilize.

Any overdose of study medication is to be reported within 24 hours of knowledge of the overdose on the Special Situations eCRF. Any AE/SAE that occurs as a result of an overdose is to be reported on the AE/SAE eCRF.

9.3.18 Pregnancy and Contraception

Female subjects of childbearing potential and males with female partners of childbearing potential must agree to use a highly effective contraceptive method (defined as achieving a failure rate of less than 1% per year) in combination with a barrier method from the time of the Screening Visit until week 12 visit (EOT) plus 5 half-lives after the last dose of A3907.

Acceptable forms of highly effective contraception include the following:

- Combined (estrogen and progestogen containing) hormonal contraception associated with inhibition of ovulation

- Progestogen-only hormonal contraception associated with inhibition of ovulation
- Intrauterine device
- Intrauterine hormone-releasing system
- Bilateral tubal occlusion
- Vasectomised partner
- Sexual abstinence defined as refraining from heterosexual intercourse during the entire period of risk associated with the study treatments
 - The reliability of sexual abstinence needs to be evaluated in relation to the duration of the clinical trial and the preferred and usual lifestyle of the subject. Periodic abstinence (e.g., calendar, ovulation, symptothermal, post-ovulation methods) and withdrawal are not acceptable methods of contraception.

Barrier methods such as condom or occlusive cap (diaphragm or cervical/vault caps) with spermicidal foam/gel/film/cream should be combined with a highly effective contraceptive method. If a pregnancy occurs in a male patient's partner at any time during the study, the pregnancy should also be reported and followed.

Women in the following categories are considered WONCBP: premenopausal female with permanent infertility due to one of the following (for the purpose of this study):

- (a) Documented hysterectomy
- (b) Documented bilateral salpingectomy
- (c) Documented bilateral oophorectomy

For individuals with permanent infertility due to an alternate medical cause other than the above, (e.g. Mullerian agenesis, androgen insensitivity, gonadal dysgenesis), investigator discretion should be applied to determining study entry.

Note: Documentation can come from the site personnel's review of the participant's medical records, medical examination, or medical history interview.

(1) Postmenopausal female

- (a) A postmenopausal state is defined as no menses for 12 months without an alternative medical cause.
 - A high FSH level in the postmenopausal range may be used to confirm a postmenopausal state in women not using hormonal contraception or hormonal replacement therapy (HRT). However, in the absence of 12 months of amenorrhea, confirmation with a FSH level ≥ 40 mIU/mL is required.

Pregnancy is not considered to be an AE. However, if the patient has been dosed with the study drug, the pregnancy must be reported on the Pregnancy eCRF within 24 hours of site awareness ([Section 9.3.4.8](#)). Date of exposure and, as far as possible, details of the period of gestation at the time of exposure must be provided.

The pregnancy should be followed up to determine outcome, including spontaneous termination, details of birth, and presence of any birth defects, congenital anomalies, or newborn or maternal complication. An infant who was exposed in-utero will be followed for up to 2 years after delivery. Any pregnancy that occurs within 90 days of the last dose of study drug must be reported to the sponsor.

9.4 Pharmacokinetic Assessments

Pharmacokinetic blood samples will be collected according to the schedule in [Table 1](#). Samples for Arms 1+2 will be obtained on Day 0 (Visit 2) and Week 12 (Visit 7) pre-dose and at 0.5, 1, 1.5, 2, 4, 6, 8, and 10 hours post-dose (\pm 5 minutes). Samples for Arms 3+4 will be obtained on Day 0 (Visit 2) pre-dose at 0.5, 1, 1.5, 2, 4, 6, 8, 12, and 24 hours post-dose (\pm 5 minutes). CCI

CCI

CCI Samples for Arms 3+4 will be obtained on Day 98 (Visit 7) pre-dose and at 0.5, 1, 1.5, 2, 4, 6, 8, and 10 hours post-dose (\pm 5 minutes). The post-dose sample collections will be obtained post administration of the first BID dose. For Visits 3 to 6 (inclusive), PK will be collected once pre-dose, and once for Visit 8. Sampling timepoints at Week 12 (Visit 7) may be adjusted based on observed data from Day 0 (Visit 2) without changing the total number of blood samples.

All pre-dose samples should be taken immediately before the administration of study drug. Patients will fast for 4 hours before study visit (only water permitted). Blood samples will be processed for collection of plasma fractions for determination of A3907 concentrations and banked for exploratory assessment of MIST (Visit 2 and Visit 7 only). In addition, a blood sample for PK analysis should be collected, if possible, at the time of any SAE.

A PK sample collection manual will be provided to instruct the type of anticoagulant, material supplies, and sample processing, storage, and shipping procedures. Plasma samples will be shipped to the analytical laboratory for analysis.

9.5 Pharmacodynamic Assessments

9.5.1 Bile Acids

Blood samples for analysis of individual and total serum bile acids will be drawn at all study visits from Visit 1 through Visit 8.

Urine samples for analysis of individual and total bile acids will be collected by the patient during the 24-hour period prior to Visits 2, 3, 5, 7, and 8. Instructions for the urine collection can be found in the laboratory manual.

For any visit at which a bile acid sample result is unreportable, an additional unscheduled visit for a repeat sample collection may be scheduled. Samples will be handled, stored, and transported to a central laboratory per instructions in the laboratory manual.

9.5.2 Serum Biomarkers

Biomarkers of liver fibrosis will be assessed, including autotaxin, ProC3, hsCRP, MMP7, MMP9, ELF score, and CA 19-9. Bile acid synthesis biomarker, C4, and FGF-19 will also be assessed. Blood samples for biomarker assessment will be collected according to [Table 1](#); samples for autotaxin, C4, and FGF-19 are to be obtained once per applicable visit, pre-dose. Details of sample handling, storage, and transportation to a central laboratory will be provided in the laboratory manual.

10 STATISTICAL EVALUATION

10.1 Sample Size and Power

Due to the exploratory nature of this study, no formal power calculations were used to determine the sample size. Approximately 24 patients are planned to be enrolled into the study.

10.2 Statistical Methods

10.2.1 Statistical Analysis Sets

Safety Analysis Set

The safety analysis set will consist of all patients who received at least 1 dose of study drug. The safety analysis set will be used for all analyses except PK and PD analyses.

Pharmacokinetic Analysis Set

The PK analysis set will include all patients who received at least 1 dose of A3907 and have evaluable PK data. The PK analysis set will be used for all PK analyses.

Pharmacodynamic Analysis Set

The PD population will include all patients who received at least 1 dose of A3907 and for whom at least 1 PD marker can be evaluated. The PD analysis set will be used for all PD analyses.

10.2.2 Methods of Statistical Analyses

10.2.2.1 General Principles

Descriptive statistics will mainly be used in this open-label study. All statistical analyses will be performed using SAS version 9.3 or higher.

In general, continuous data will be summarised using the number of observations available, mean, standard deviation (SD), median, minimum, and maximum. Categorical and ordinal data will be summarised using the count and percentage of patients.

10.2.2.2 Missing Data

Missing data will be reported descriptively. In general, imputations of missing observations will not be made. Any additional analysis concerning missingness and details regarding handling of missing data will be described in the statistical analysis plan (SAP).

10.2.2.3 Demographic and Baseline Characteristics

Descriptive summaries of demographics and other baseline characteristics, including medical and surgical history, will be presented overall using the safety analysis set. Prior medication will be summarised overall using the safety analysis set.

10.2.2.4 Patient Disposition

The following will be summarised overall by treatment arm:

- Patients enrolled (who signed the informed consent)
- Patients treated
- Patients discontinuing the treatment permanently (including reason for discontinuation)
- Patients completing the study
- Patients withdrawing early (including withdrawal reason)

Additionally, patients enrolled, included in the safety analysis set will be summarised by region by treatment arm.

10.2.2.5 Safety Analysis

Safety data will be analyzed using descriptive statistics and overall summaries of AEs, SAEs, ECG, vital signs, physical examinations, clinical laboratory tests (hematology, clinical chemistry, urinalysis, and coagulation), and concomitant medication. Analyses will be performed using the safety analysis set.

Summaries of AEs (coded according to Medical Dictionary for Regulatory Activities [MedDRA] system organ class and preferred term) will include:

- Overview of the incidence of all AEs (AEs, Drug-related AEs, AEs leading to study discontinuation),
- TEAEs by system organ class (SOC) and preferred term (TEAEs, Drug-related TEAEs, TEAEs leading to study discontinuation),
- Intensity/severity of TEAEs by SOC and preferred term,
- Drug-related TEAEs by SOC and preferred term,
- TEAEs leading to study discontinuation by SOC and preferred term, and
- Treatment-emergent SAEs by SOC and preferred term.

Summaries of TEAEs will be presented separately by the single dose (Day 0 to Day 13) and 12-week (Day 14 to Day 112) treatment periods.

Concomitant medication use during the Treatment Period will be summarised by Anatomical Therapeutic Chemical (ATC) class and World Health Organization (WHO) preferred name.

Summaries of vital signs and clinical safety laboratories will be presented. For each visit, the actual results, the change from baseline, and the number and percentage of patients with potentially clinically significant values observed post-baseline will be presented.

Data listings will be provided for each patient for all safety parameters.

10.2.2.6 Compliance and Exposure

Treatment Compliance = $100 \times ([\text{Number of study drug dispensed} - \text{number of study drug returned}] / \text{number of study drug that should be taken})$.

10.2.2.7 Pharmacokinetic Analysis

The PK analysis will be conducted employing noncompartmental methods using WinNonlin®. Only patients who are given A3907 and have evaluable plasma concentration-time profiles will be included in the analysis.

Individual A3907 plasma concentrations at specified timepoints will be listed for each patient and will be summarised by dose level. Individual plasma concentration-time profiles of A3907 will be plotted on both a linear and a semi-logarithmic scale for each dose level. Mean values will also be presented graphically for each dose level.

The following PK parameters may be determined for A3907 unless otherwise specified:

- C_{\max} : Maximum plasma concentration
- T_{\max} : Time of maximum plasma concentration
- $t_{1/2}$: Elimination half-life
- AUC_{0-t} : Area under the plasma concentration-time curve from time zero to time t (time of last quantifiable plasma concentration)
- AUC_{∞} : Area under the plasma concentration-time curve from time zero to infinity

Additional details on the computation of the PK parameters will be provided in a separate analysis plan. Analysis and results of potential exploratory analyses of A3907 metabolites in plasma samples will be reported outside the Clinical Study Report for the study.

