5.2.2 PSC with Clinically Relevant Stricture

Strictures are a common radiographic finding in PSC. Dominant strictures are defined as a biliary stricture observed on ERCP with a diameter of ≤ 1.5 mm in the common bile duct or of ≤ 1 mm in the hepatic duct with further delineation in the definition as a high-grade stricture when there is a $> 75\%$ reduction in the common bile duct on magnetic resonance imaging (MRI) ([Bowlus et al., 2023](#)). A clinically relevant stricture is a high-grade biliary stricture on imaging in the common bile duct or hepatic ducts with signs or symptoms of obstructive cholestasis and/or bacterial cholangitis. A clinically relevant stricture is a high-grade biliary stricture on imaging in the common bile duct or hepatic ducts with signs or symptoms of obstructive cholestasis and/or bacterial cholangitis. Forty (40) to 58% of patients with PSC will develop radiographically apparent strictures ([Aljiffry et al., 2011](#)) and

in 15 to 20% of patients with PSC ([Hilscher et al., 2018](#)), a localized CRS is the most prominent feature at diagnosis. Individuals with CRS may be considered a different population in PSC and could be stratified as a cohort separate from those who do not have CRS. The presence of an untreated CRS, even in the absence of bile duct malignancy, has been associated with more advanced liver disease histologically, increased liver stiffness assessment via Fibroscan, facilitation of bacterial colonization, increased risk for cholangiocarcinoma, significantly reduced survival, and, if the stricture is accompanied by high-grade dysplasia, earlier liver transplantation should be considered ([EASL, 2022](#)).

Patients with CRS's are often excluded from PSC clinical trials, especially if a biliary intervention (stent, dilatation) has occurred within the 3 months prior to the Screening Visit. Clinically relevant strictures are typically managed by endoscopic or surgical interventions such as stenting, or dilatation, or resection. These procedures are not without risk and can include recurrent bleeding, infection, bacterial cholangitis, perforation, or pancreatitis. Balloon dilatations of CRS usually need to be repeated at intervals of 1 to 4 weeks; there is no consensus agreement on dilation protocols; and no results are reported in clinical or biochemical improvement after repeat dilations ([EASL, 2022](#); [European Society of Gastrointestinal et al., 2017](#)).

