5.4 Dose Rationale

A3907 has been extensively evaluated in nonclinical studies and has been shown in vitro and in vivo to effectively inhibit ASBT. The dose selected for this study is based on data collected in nonclinical studies, as well as safety data generated from the FIH study (A3907-001).

In Study A3907-001, A3907 in a capsule formulation was administered to healthy subjects in single doses (SAD) ranging from ■ mg to ■■■ mg, and multiple doses (MAD) ranging from ■■■ up to ■■■ for 7 days. Administration of A3907 was well tolerated after single and 7-day repeated doses, and there were no clinically relevant safety findings at any of the dose levels. In the SAD study, the geometric mean of C_{max} and AUC were ■■ ng/mL and ■■ ng h/mL respectively, and the highest C_{max} and AUC values were ■■ ng/mL and ■■ ng h/mL respectively. In the MAD study, a mean C_{max} of ■■ ng/mL and AUC of ■■ ng h/mL was observed at the ■■ dose at steady state. Pharmacodynamic effects were observed with an increase in C4, a biomarker of bile acid synthesis; a reduction in LDL-C; and a post-prandial increase in serum bile acids at all A3907 dose levels administered for 7 days.

In this 12-week study, A3907 doses of 10 and 30 mg QD (Arms 1 and 2, respectively), and 30 mg BID (Arms 3 and 4) in a tablet formulation will be administered to 6 patients per arm.

■■■

■■■

These doses are expected to result in exposures predicted to be pharmacodynamically active based on pre-clinical mouse disease models. A3907 has been administered orally for three months to rats and dogs in toxicology studies at doses up to ■■ mg/kg/day, respectively, with no adverse findings at any of the dose levels explored. ■■■

CCI

CCI

). In this study, individual PK values may vary due to factors such as gastrointestinal transit time, presence of food, volume of contents within the gastrointestinal tract, and liver impairment. Additionally, A3907 will be administered in a tablet formulation. CCI

CCI

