7 INVESTIGATIONAL PLAN

7.1 Overall Study Design and Plan

7.1.1 Description

This is an open-label, Phase 2 study to evaluate the safety, tolerability, PK, and PD effects of 3 dose levels of A3907, 10 mg (Arm 1), 30 mg (Arm 2) administered orally QD, or 30 mg BID in Arms 3 and 4 for 12 weeks in patients with PSC with and without a CRS (Figure 1). Eligible patients must have a clinical diagnosis of large-duct- PSC as evidenced by chronic cholestasis of more than 6 months duration. Patients must also have serum bile acids above the upper limit of normal (ULN) at the Screening Visit and ALP levels $> 1.5 \times \text{ULN}$ but $\leq 10 \times \text{ULN}$ repeated at least 2 weeks apart for baseline to reflect variability of $< 30\%$. If variability is $> 30\%$, a third ALP level may be obtained to determine the direction of abnormality or document stability. If stable ($< 30\%$ variance) the patient may be enrolled.

Prior to any other study procedures being conducted, the patient will have the nature of the study explained to him/her and be asked to sign an informed consent form (ICF). Informed consent must be obtained prior to any study procedures that do not form a part of the patient's normal care. After signing the ICF, patients will be evaluated for study eligibility. If not fasting at time of consent, patient will return to complete screening assessments after having fasted for 4 hours.

The study includes up to a 2-week Screening Period, followed by administration of a single dose of A3907, followed by a 2-week period to confirm the target exposure is reached before beginning a treatment period of 12 weeks. Each patient's PK will be reviewed and, if the systemic exposures do not exceed the highest systemic exposure previously established in the SAD portion of the FIH study CCI

CCI the dose will be confirmed and the patient will begin administration of A3907 daily for 12 weeks. If the exposures exceed the highest systemic exposure, the individual patient will be terminated early.

Enrollment into the treatment arms will be staggered with Arm 2 beginning after at least 3 patients in Arm 1 have completed 2 weeks of treatment and an internal Safety Review Committee (SRC) has reviewed safety and PK data. Enrollment into Arms 3 and 4 will occur

[figure not shown]
concurrently beginning after at least 3 patients in Arm 2 have completed 2 weeks of treatment and an internal SRC has reviewed safety and PK data.

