8.1. Pharmacokinetic Analysis

PK analyses will be described in separate analysis plans, and results will be reported outside the Clinical Study Report for the study.

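### Grouping A3907 concentrations by dose level merges Arms 3 and 4, so the planned PK summaries would mask any exposure difference between patients with and without a stricture

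*Protocol*

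**What the plan says.** Protocol 10.2.2.7 sets the grouping for concentrations: "Individual A3907 plasma concentrations at specified timepoints will be listed for each patient and will be summarised by dose level". For the plots it says: "Individual plasma concentration-time profiles of A3907 will be plotted on both a linear and a semi-logarithmic scale for each dose level", and then: "Mean values will also be presented graphically for each dose level". The synopsis repeats all three statements.

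Protocol 7.1.1 describes "3 dose levels of A3907" and gives "30 mg BID in Arms 3 and 4 for 12 weeks in patients with PSC with and without a CRS". Arms 3 and 4 therefore differ in CRS status but not in dose. Protocol 7.2.1 plans six patients in each of the four arms.

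Two passages in the protocol give reasons to expect that exposure might differ between these arms. Section 5.4 warns: "individual PK values may vary due to factors such as gastrointestinal transit time, presence of food, volume of contents within the gastrointestinal tract, and liver" (the last factor in that list is impaired liver function). Section 5.2.2 says of stricture patients: "Individuals with CRS may be considered a different population in PSC and could be stratified as a cohort separate from those who do not" (meaning those without a stricture). In addition, inclusion criterion 6 limits total and direct bilirubin in Arms 1 to 3 only.

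SAP section 4 sets treatment arm as the general basis for descriptive statistics. On PK, however, SAP 8.1 says only: "PK analyses will be described in separate analysis plans, and results will be reported outside the Clinical Study Report for the study". SAP section 11, which lists departures from the protocol, does not mention PK grouping.

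**The concern.** The protocol keeps arm and dose level apart as terms. Where it means arm it says so, as for patient disposition in 10.2.2.4. A PK programmer following 10.2.2.7 as written would produce three groups, the third being half patients with a stricture and half without.

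Three things are at stake.

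- The 30 mg BID summary and mean curve could describe neither population well. An Arm 4 versus Arm 3 difference would not appear in any planned summary.
- Any reading across dose levels would mix dose with disease, because CRS patients enter only at the top level.
- TEAEs are tabulated by arm (SAP 9.1), and PD follows the SAP's general by-arm rule. Arm 4's safety and PD columns would then have no matching exposure column, although the primary objective covers patients with and without a CRS.

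**Working it through.** **Group sizes.** 4 arms × 6 patients = 24, which matches the planned total. By dose level the groups are 6, 6 and 6 + 6 = 12; by arm they are 6, 6, 6 and 6. These are approximate: withdrawn patients may be replaced, and the PK set takes anyone with one dose and evaluable data.

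**Effect of pooling on the centre.** Let R be Arm 4 exposure divided by Arm 3 exposure. The readable text gives no value for R, so it is an assumption, shown here on both sides of 1. With n₃ and n₄ patients, the pooled geometric mean is Arm 3 × R^(n₄/(n₃+n₄)), which is Arm 3 × √R when n₃ = n₄. Relative to Arm 4 it is 1/√R. Protocol 10.2.2.1 names the arithmetic mean as the general statistic; its pooled value is Arm 3 × (1 + R)/2.

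| R (assumed) | Pooled geometric mean ÷ Arm 3 (√R) | Pooled geometric mean ÷ Arm 4 (1/√R) | Pooled arithmetic mean ÷ Arm 3 ((1+R)/2) |
|---|---|---|---|
| 0.5 | 0.71 | 1.41 | 0.75 |
| 1 | 1.00 | 1.00 | 1.00 |
| 1.5 | 1.22 | 0.82 | 1.25 |
| 2 | 1.41 | 0.71 | 1.50 |

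**Effect on the spread.** With within-arm log variance s² = ln(1 + CV²), the expected log variance of the pooled 12 is s² + 3(ln R)²/11. At an assumed CV of 50%, s² = ln(1.25) = 0.223. At R = 2 the pooled variance is 0.223 + 3 × 0.480/11 = 0.354, an apparent CV of √(e^0.354 − 1) = 65%.

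**Effect on reading across doses.** If the true Arm 3 / Arm 2 ratio is X, the step from the 30 mg QD row to the pooled 30 mg BID row shows X√R. At R = 2, 41% of apparent extra rise comes from CRS status, not dose.

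**What a by-arm comparison could show.** The 95% interval for the Arm 4 / Arm 3 geometric mean ratio is the estimate multiplied or divided by exp(t × s × √(2/6)), with t = 2.228 on 10 degrees of freedom. At CV 50%, s = 0.472, so the factor is exp(2.228 × 0.472 × 0.577) = 1.84. The same formula gives 1.46 at CV 30% and 2.47 at CV 80%. The CVs are assumptions.

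**The case against.** The strongest reply is that the grouping may already be settled elsewhere. SAP 8.1 sends PK to separate plans, the SAP's default is by arm, and 10.2.2.7 states no grouping for Cmax and AUC, which are the named PK parameters of the secondary endpoint. This stands in part: the pooling is a literal reading of the concentration and plot sentences, and a plan not seen here could split the arms. It does not remove the point. The only stated PK grouping is by dose level, and what 10.2.2.7 defers is how parameters are computed, not how patients are grouped.

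Several stronger readings are tempting but not supported.

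- *The plan hides any exposure difference.* It does not. Concentrations are listed per patient and individual profiles are plotted, so with six patients per arm Arm 4 can be picked out by hand.
- *A planned dose-proportionality analysis is biased.* Neither document plans one. The mixing of dose and disease affects whatever a reader infers across the rows.
- *Dosing decisions in the trial rest on the pooled mean.* They do not. Entry to 12-week treatment uses each patient's own Cmax and AUC, and both SRC enrolment gates come before Arms 3 and 4 open.
- *The Arm 4 limit of MELD below 35 proves severe impairment.* INR above 1.3 and GFR below 60 are excluded in every arm. With INR 1.3 and creatinine 1.0 mg/dL (assumed), the protocol's formula gives 11.2 × ln(1.3) + 6.43 = 9.37, plus 3.78 × ln(bilirubin). A score of 34 would need bilirubin of about 676 mg/dL. The absent bilirubin limit is the sounder evidence that Arm 4 may differ.

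**Conclusion.** The point holds as a reporting defect, with moderate confidence because the PK plan is not available. As written, concentration summaries and mean plots combine Arms 3 and 4, and nothing in either document commits to showing PK by arm or CRS status. The size depends wholly on R: none at R = 1, and a pooled geometric mean 22% above Arm 3 and 18% below Arm 4 at R = 1.5. The direction reverses if Arm 4 exposure is lower. The documents do not show that R differs from 1; they give reasons why it might, and the planned summaries could not tell the reader which case applies. Sample size and error rates are unaffected, since the study is descriptive.

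**What to change.** In the PK analysis plan, state that concentrations, Cmax, AUC and mean plots are summarised by treatment arm, with Arms 3 and 4 separate. Base any dose-exposure description on Arms 1 to 3. Keep a pooled 30 mg BID row only as supportive. An Arm 4 / Arm 3 geometric mean ratio with 95% CI may be added, labelled descriptive. Align Protocol 10.2.2.7 and the synopsis at the next amendment; the PK plan can carry the change meanwhile. By-arm wording also stays unambiguous if the SRC adjusts doses in Arm 3 or Arm 4, as Protocol 8.2 allows.

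No new patients or samples are needed, only one more column. The cost is precision. At an assumed CV of 50%, the 95% interval for a 30 mg BID geometric mean widens from a factor of exp(2.201 × 0.472/√12) = 1.35 with 12 patients (taking R = 1) to exp(2.571 × 0.472/√6) = 1.64 with 6. The arm ratio, at about ×/÷ 1.84, would show only large differences.
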